Title: A Mobile App Based Cognitive Dissonance Intervention for Smoking Cessation

NCT Number: NCT05797155

Date: 3/15/2025

The study included a group-delivered intervention and an ungrouped control condition, creating a partially nested design. The models allowed for between-cluster variability in the outcomes solely within the intervention group to reflect the partial clustering of the data (Baldwin et. al., 2011). Logistic regression models were estimated with a binomial distribution and logit link using the SAS software (Version 9.4) with SAS PROC GLIMMIX and used to test for condition differences (1 =  $S2Q$ , 0 = control), separately at 1- and 3-month follow-up, for the dichotomous outcomes. Odds ratios (ORs) were reported as a measure of effect size, following conventional benchmarks: 1.5 (small), 2.5 (medium), and 4.3 (large; Chen et al., 2010). To address missing data, models were estimated with 20 imputed datasets using SAS PROC MI, and results were combined using SAS PROC MIANALYZE. Mixed-effects growth models were used to evaluate condition differences in the continuous Fagerstrom outcome. The baseline was defined as the random intercept, and the model included fixed effects variables for time, measured in months since the baseline assessment, the randomized condition variable (1 =  $S2Q$ , 0 = control), and a time-by-condition interaction term. The interaction term estimates the change in the outcome from baseline to 3-month follow-up for the intervention condition relative to the control condition. Models were estimated with maximum likelihood using all available data. Cohen's  $d$  was provided as a measure of effect size using conventions: 0.2 (small), 0.5 (medium), and 0.8 (large).

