## C. APPROACH

### C.1. Product evaluation.

We will conduct an evaluation of the CoQuit app with a nationwide sample of 500 adults who are daily smokers. Feasibility, usability, participant satisfaction, and intervention outcomes of cigarette use will be evaluated in an efficacy trial. Data on: 1) frequency and duration of app use, 2) number of modules completed, 3) changes in measures of cognitive dissonance, 4) changes in readiness to quit, and 4) changes in smoking attitudes and behaviors (including quit attempts, number of days without smoking, and co-use of other forms of tobacco, including e-cigarettes) will be examined. Participants will be compensated using gift cards to Amazon with \$25 each for the baseline, 1-month and for the 3-month assessment. In addition, each participant who completes all three assessments will receive a bonus payment of \$50. We estimate that 75% of participants will receive the bonus payments. Participants in the focus groups and usability testing will receive a \$50 gift card for their time and effort.

**C.2. Study Design.** Our evaluation of the CoQuit app will be conducted with 500 adults who are daily smokers who will be recruited through social media. Participants will be randomly and equally assigned to one of two conditions: 1) CoQuit with CDI (cognitive dissonance induction), or 2) CoQuit content without CDI. All participants will be instructed to attempt to reduce cigarette use and to identify a target quit date at program initiation. Self-reported cigarette use and readiness to quit will be measured at 1-month and 3-month assessments. In addition, we will measure changes in cognitive dissonance for participants in the CoQuit CDI group. Cognitive dissonance measures will be completed after each cognitive dissonance activity, as well as at each of the baseline, 1-month and 3-month assessments.

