### C.4. Overview of the Proposed Intervention Conditions

We propose to randomize participants into one of two conditions, outlined below.

**CoQuit with CDI.** Participants who are randomized to the CoQuit with CDI will be sent access information and instructions and access code for downloading the CoQuit CDI app from the app store immediately following their baseline assessment. Once the app is loaded onto their phone, participants will be assigned to a group of 8 daily smokers who are intended to move through the app at a similar pace. The proposed modules will each include an instruction video that outlines a cognitive dissonance inducing activity that participants will be instructed to record and upload to the app for all group members to see. Modules will be “unlocked” in ascending order as participants move through the program (i.e., module 2 will be “unlocked” after a participant completes module 1, etc.). In addition, participants will receive 2 smoking cessations tips per day to assist with reducing cigarette use and increasing motivation to quit.

**CoQuit without CDI (comparison condition)** Participants who are randomized to the CoQuit without CDI will be sent access information, instructions and an access code for downloading the CoQuit app from the app store immediately following their baseline assessment. Once the app is loaded onto their phone, participants will be free to login and use the app as often as they want. Daily tips and guidance in reducing smoking and increasing motivation to quit will be provided at least once daily. The content and look and feel of this comparison condition will match the CoQuit with CDI but lack any cognitive dissonance activities.

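### The Fagerström growth model names only a random intercept at baseline, so the SAP does not show that clustering by peer group, which can arise only after baseline, enters the tested time-by-condition interaction

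*SAP*

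**What the plan says.** The SAP describes the trial as partially nested: "The study included a group-delivered intervention and an ungrouped control condition, creating a partially nested design". It then makes a general statement, placed before either type of model is described: "The models allowed for between-cluster variability in the outcomes solely within the intervention group".

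For the continuous Fagerström outcome it describes a growth model over months since baseline. The one random effect named there is in the phrase "The baseline was defined as the random intercept"; its level, participant or group, is not given. Time, condition and their product are listed as fixed effects. The product term is the tested effect and is read as the difference between arms in change to month 3. No random slope is named at either level.

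Protocol C.4 gives the timing of the groups. Intervention participants receive what they need for "downloading the CoQuit CDI app from the app store immediately following their baseline assessment", and the next step is that "participants will be assigned to a group of 8 daily smokers who are intended to move through the app at a similar pace". The group therefore comes into being after the baseline score has been recorded.

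**The concern.** A peer group that does not yet exist cannot influence a baseline score. Groups may differ at baseline through who happens to be in them, but the influence that the partially nested model is meant to capture acts on scores after baseline, and so on change.

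A group random intercept adds the same constant to a member's scores at 0, 1 and 3 months. It describes stable differences between groups and says nothing about groups changing at different rates. A model with such a term could truthfully be said to allow between-cluster variability, yet still test the interaction as if S2Q participants changed independently of each other. A participant random slope would not repair this, because it treats members of one group as independent in their change.

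At stake is the validity of the Fagerström interaction test. If groups differ in change, the standard error is too small and false positives exceed the nominal rate.

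**Working it through.** The documents give no ICC, significance level, SD or power figure for this outcome, so there is no stated figure to reproduce. The check asks what follows if the random effects are only those named.

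**Inputs from the documents**
- Sample: "nationwide sample of 500 adults who are daily smokers" (protocol C.1).
- Allocation: "Participants will be randomly and equally assigned to one of two conditions" (protocol C.2), so 500/2 = 250 per arm.
- Group size 8 in the intervention arm (protocol C.4): 250/8 = 31.25, about 31 groups.
- Protocol C.1 expects 75% to complete all three assessments: 0.75 × 8 = 6, used as a lower group size.
- Assessments at 0, 1 and 3 months.

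**Assumptions**
- Group ICC of change (the share of the variance of participants' slopes in the S2Q arm that lies between groups) of 0.02, 0.05 or 0.10.
- Two-sided nominal level of 5%, complete data, and equal slope variance in the two arms.

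**Step 1: a group intercept cancels.** The mean time is 4/3, so the centred times are −4/3, −1/3 and 5/3, which sum to 0. A participant's fitted slope is Σ(t − t̄)y / Σ(t − t̄)². A constant group effect u contributes u × 0 / Σ(t − t̄)² = 0. With complete data it drops out of every slope, and hence out of the interaction and its standard error.

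**Step 2: the size of the omission.** Let V be the slope variance, n the number per arm and m the group size.
- Design effect in S2Q: DE = 1 + (m − 1) × ICC.
- True variance of the difference in slopes: (V/n)(DE + 1). If groups are ignored: 2V/n.
- Variance ratio: R = (DE + 1)/2.
- Actual type I error: 2[1 − Φ(1.96/√R)].

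| m | ICC | DE | R | √R | Type I error |
|---|---|---|---|---|---|
| 8 | 0 | 1.00 | 1.000 | 1.000 | 5.0% |
| 8 | 0.02 | 1.14 | 1.070 | 1.034 | 5.8% |
| 8 | 0.05 | 1.35 | 1.175 | 1.084 | 7.1% |
| 8 | 0.10 | 1.70 | 1.350 | 1.162 | 9.2% |
| 6 | 0.02 | 1.10 | 1.050 | 1.025 | 5.6% |
| 6 | 0.05 | 1.25 | 1.125 | 1.061 | 6.5% |
| 6 | 0.10 | 1.50 | 1.250 | 1.118 | 8.0% |

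√R is the factor by which the true standard error exceeds the one that ignores groups.

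**Step 3: simulation.** 4,000 null trials per setting, 31 groups of 8 against 250 ungrouped controls, complete data.
- Random intercepts only, no other participant-level slope variance: 5.5%, 7.7% and 9.8% at ICC 0.02, 0.05 and 0.10.
- Participant slope but no group slope: 5.5–5.7%, 7.3% and 8.8–9.0%.
- Group-level slope in S2Q only, with Satterthwaite df: 4.2–5.8% over ICC 0 to 0.10.

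The Monte Carlo standard error near 5% is √(0.05 × 0.95/4000) = 0.3 points, so the first two lines agree with the closed form to within about twice that.

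**The case against.** The strongest reply is that silence is being read as absence. The sentence on between-cluster variability covers the models without exception and could include a group slope that was fitted but not described. The phrase about baseline may only say where time zero lies; it is not presented as a full list of random effects. The SAP also cites a methods paper for the partially nested specification, which cannot be consulted here. This stands in part. A reader might infer that clustering in change was certainly missed, and the documents do not support that. They show a model whose named terms would leave it out, and a general statement that does not settle the question.

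The size is also open to challenge. The ICCs are assumed. Full groups of 8 are the upper case. Group assignment follows loading of the app, so S2Q participants who never load it have no group, which dilutes the clustering. All of this stands, and it is why the range with 6 per group and the zero case are shown.

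A reader might reach larger figures by adding a participant-level misspecification. In the simulation, intercepts only with 30% of slope variance between participants already gave 6.4% at group ICC 0. That excess is a separate matter and should not be attributed to groups.

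Finally, the scope is narrow. The dichotomous outcomes, including the cessation outcomes on which protocol C.5.1 focuses the 3-month assessment, are modelled separately at 1 and 3 months. By then the groups exist, and a group intercept captures their clustering. A reader might infer that the cessation results share this weakness; they do not.

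**Conclusion.** The point holds as an incomplete specification with a definite consequence. If the Fagerström model contains only the random effect that the SAP names, with or without a group intercept beside it, the interaction test ignores group clustering in change.

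The consequence is small at an ICC of change of 0.02 and material at 0.05 to 0.10: false positives of roughly 6.5–7.1% and 8.0–9.2% respectively, across 6 to 8 per group, in place of 5%. These figures rest on assumed ICCs, complete data, equal slope variances and all S2Q participants being grouped. Whether a group slope was in fact fitted cannot be told from the documents.

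**What to change.** State, for the Fagerström model, the level (participant or group) and the term (intercept or time) of each random effect. In the S2Q arm only, specify a group random slope on time, or equivalently in purpose a group effect fixed at zero at baseline and free afterwards. Keep it separate from the participant-level covariance. Name a small-sample df method such as Satterthwaite, since only about 31 groups inform the group variance, and say how S2Q participants who never joined a group are coded.

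The SAP is written in the past tense, so first check the analysis code. If the term was fitted, a sentence in the SAP suffices; if not, refit and report that result.

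The cost is a few lines of SAP text and one RANDOM statement. The interval for the interaction becomes slightly wider: at 8 per group, by a factor of about 1.03 at ICC 0.02 and 1.16 at ICC 0.10, before any change in df.

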A full description of measures is included in the Human Subjects. Briefly, the following will be used to examine pre- and post- changes in smoking behavior, cognitive dissonance, and motivation to quit: 1) Nicotine Dependence, 2) Past and Current Tobacco Use (including e-cigarettes), 3) Motivation to Quit, 4) Quit Attempts, and 5) Cognitive Dissonance. Nicotine dependence will be measured at baseline and at each follow-up assessment using the Fagerström Test for Nicotine Dependence and items that assess withdrawal experiences. Past and current tobacco use will be assessed at each time point, including type (including e-cigarettes), frequency, and duration of use. Motivation to quit will be assessed at baseline by asking participants if they want to quit within the next 30 days and at follow-up assessments in terms of stages of change. We will also use an adaptation of the Contemplation Ladder that we have used extensively in our prior research and have found in predicting tobacco cessation. Quit attempts will be measured by the number of intentional quit attempts that last at least 24 hours, duration of quitting, and use of pharmacological adjuncts at each time point. Cognitive dissonance will be measured using the Dissonance Thermometer. Prior research has shown that the 3-item discomfort factor of the Dissonance Thermometer represents the affective expression of cognitive dissonance. Cognitive dissonance will be assessed after each cognitive dissonance activity, as well as at each of the baseline, 1-month and 3-month assessments.

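### The 1- and 3-month logistic models name no baseline covariate; adjusting for measures already collected is a cheap, conditional gain in efficiency, not the repair of an error

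*SAP*

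**What the plan says.** **Logistic models.** The SAP uses logistic regression "with SAS PROC GLIMMIX and used to test for condition differences", coded 1 for S2Q and 0 for control, with a separate model at each follow-up. On clustering it says: "The models allowed for between-cluster variability in the outcomes solely within the intervention group". No other predictor is named. The SAP does not say outright that the models are unadjusted.

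**Growth model.** For the continuous Fagerström outcome the same paragraph is explicit: "the model included fixed effects variables for time, measured in months since the baseline assessment, the randomized condition variable", followed by a time-by-condition interaction. Baseline enters there as the first repeated measurement.

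**Missing data.** For the dichotomous outcomes, "models were estimated with 20 imputed datasets using SAS PROC MI". The variables in the imputation model are not listed.

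**Baseline data.** Protocol section C.5.2 says "Nicotine dependence will be measured at baseline and at each follow-up assessment", "Past and current tobacco use will be assessed at each time point" and "Motivation to quit will be assessed at baseline by asking participants if they want to quit within the next 30 days". Section C.5.1 lists readiness to quit in the baseline assessment. Section C.5.2 adds that an adapted Contemplation Ladder has been found, in the team's earlier research, to predict cessation. It gives no strength of association and does not state the visits at which the ladder is given.

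**The concern.** Cessation is the central outcome, yet as written its models make no use of the baseline information that the trial pays to collect. If dependence, amount smoked or readiness predict quitting, an adjusted test has somewhat more power at the same sample size, and a standardised (marginal) effect has a smaller variance. The documents state no power target, so there is no stated margin that would make this irrelevant. What is at stake is efficiency and a fully specified model. The validity of the comparison is not in question.

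**Working it through.** **There is no planned figure to reproduce.** The documents give 500 participants with equal allocation (C.2), so 250 per arm, and intervention groups of 8 (C.4). They give no alpha, power, target effect, control quit rate, intraclass correlation or prognostic strength.

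**Assumptions (not in the documents).** Two-sided alpha 0.05; quit rates 15% and 25%; latent intraclass correlation 0.05 in the intervention arm; Fagerström score and amount smoked standard normal with correlation 0.6 and equal coefficients; combined logit SD 0, 0.3, 0.6 or 0.9 (AUC 0.50, 0.58, 0.66, 0.72); a yes/no motivation item (90% yes) with no effect.

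**Derived quantities.**
- Random-intercept variance: (0.05/0.95) × π²/3 = 0.173.
- Intervention groups: 31 × 8 + 2 = 250.
- Marginal odds ratio: (0.25/0.75)/(0.15/0.85) = 1.89; log 0.636.

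**Hand check of unadjusted power.** The variance of the log odds ratio is 1/(250 × 0.15 × 0.85) + D/(250 × 0.25 × 0.75) = 0.0314 + 0.0213D, where D is the design effect in the intervention arm.
- D = 1: SE 0.230, z = 2.77, power Φ(2.77 − 1.96) = 79%.
- D = 1 + 7 × 0.05 = 1.35: SE 0.245, z = 2.59, power 74%.

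The correlation on the observed binary scale is below the latent 0.05, so a value between the two is expected. The simulated 76 to 77% fits.

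**Simulated power, unadjusted to adjusted (%).**

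| Logit SD | Cluster-robust logistic (40,000 trials) | Intervention-arm random intercept (4,000 trials) | Cluster-robust, 25% missing, 20 imputations (6,000 trials) |
|---|---|---|---|
| 0 | 76.4 to 76.2 (−0.2) | 67.1 to 66.6 (−0.5) | 65.0 to 64.8 (−0.3) |
| 0.3 | 76.6 to 76.9 (+0.3) | 67.9 to 67.9 (+0.1) | 66.2 to 66.5 (+0.3) |
| 0.6 | 77.1 to 79.0 (+1.9) | 67.8 to 69.9 (+2.1) | 67.1 to 68.8 (+1.6) |
| 0.9 | 77.3 to 81.1 (+3.8) | 68.9 to 74.0 (+5.2) | 67.8 to 71.7 (+3.8) |

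Changes are taken before rounding. The Monte Carlo SE of the change is up to 0.14, 0.5 and 0.4 points respectively. In the last column both analyses impute with the baseline variables. The 25% missing is an upper bound for one visit, because C.1 expects 75% to complete all three assessments. Two smaller runs of the cluster-robust case gave −0.4, +0.4, +2.0, +3.9 (8,000 trials) and 0.0, +0.4, +1.9, +4.2 (4,000 trials).

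**Cross-check from variances.** In the cluster-robust case, the variance of the standardised log odds ratio relative to unadjusted is 1.003, 0.996, 0.960 and 0.906. Adjusted power should be near Φ(z/√ratio − 1.96).
- Logit SD 0.9: unadjusted 77.3% implies z = 2.709; 2.709/√0.906 = 2.846; power 81.2% (simulated 81.1%).
- Logit SD 0.6: 2.702/√0.960 = 2.758; power 78.8% (simulated 79.0%).

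In participants, 500 × (1/ratio − 1) gives −1.5, +2, +21 and +52.

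**Scale.** The SE of the covariate-conditional log odds ratio rises, to 1.01, 1.02, 1.04 and 1.08 times the unadjusted SE. The gain in precision therefore appears only after standardisation.

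**Other inputs (cluster-robust, logit SD 0.3 to 0.9).** 10% against 19%: +0.1 to +2.9 points. 20% against 31%: +0.6 to +4.5. A separate simulation without clustering or missing data, with three independent covariates, control rates of 10 to 30% and odds ratios of 1.5 to 2.0, gave −0.7 to +0.8 with no prognostic value, +0.5 to +2.6 at logit SD 0.5, +2.4 to +4.2 at 0.8 and +3.4 to +8.2 at 1.0.

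**The case against.** **Preference, not defect.** Randomisation supports the unadjusted test, and the growth model is no precedent for adjustment: it also lists no further covariate, and its baseline value enters as part of the outcome series. Both statements stand.

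**The size rests on assumptions.** The gain of 2 points or more needs logit SD 0.6 to 0.9; at 0.3 it is 0.1 to 0.3. Everyone enrolled smokes daily and has expressed a desire to quit (C.3), which may narrow the covariates. The +5.2 comes only from the random-intercept model, whose rejection rate under equal quit rates was 3.5 to 4.5%. No run combines a random intercept with imputation, and the SAP does not name the GLIMMIX estimation method. All of this stands and limits the claim to a conditional one.

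**Timing.** The SAP is dated 3/15/2025 and written in the past tense. If outcomes had been seen before covariates were chosen, adjustment cannot become primary. This stands and is carried into the fix.

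**Stronger readings that the documents do not support.**
- A reader might infer that the odds ratios are misread against the SAP's effect-size benchmarks because they are cluster-specific or conditional. The SAP says "Odds ratios (ORs) were reported as a measure of effect size, following conventional benchmarks", but never states the scale on which those benchmarks are defined, and its wording on clustering does not settle whether the odds ratio is cluster-specific.
- A reader might infer that any gain must come from dependence and amount smoked. Those carry the effect in the simulation by assumption only. The one predictive claim in the protocol concerns the Contemplation Ladder.
- A reader might take half a point as the most that adjustment can cost. It is a simulation estimate and not a bound; one scenario without clustering gave −0.7.

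**Conclusion.** The point holds as a cheap improvement. The SAP names no baseline covariate for the cessation models, although plausible ones are collected. With 250 per arm and assumed quit rates of 15% and 25%, the change in power is about 0 points if the measures are weakly prognostic, and a loss of a few tenths of a point is possible. It is about 2 to 4 points under a cluster-robust analysis, and up to about 5 under a random-intercept model, if they are moderately to strongly prognostic. Quit rates, intraclass correlation and prognostic strength are all assumed, and the eligibility criteria may put the true gain at the low end. The text does not support calling the unadjusted analysis biased or invalid.

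**What to change.** State whether the logistic models are adjusted. Preferably:

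- Add baseline Fagerström score, baseline amount smoked and the baseline motivation or readiness measure (the Contemplation Ladder if it was given at baseline) as fixed covariates at 1 and 3 months. Amount smoked is the useful form, because daily smoking is universal by eligibility.
- Keep the intervention-arm cluster term.
- List the same variables in PROC MI.
- Report a standardised risk difference or odds ratio beside the unadjusted result, and label the covariate-adjusted odds ratio as conditional.
- Say when the covariates were chosen. If that was not before outcome data were seen, keep the unadjusted model as primary and label the adjusted model a sensitivity analysis. The primary test then gains no power.

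**Cost.** No new data and a few sentences of SAP text. Some programming is needed for standardised effects with valid standard errors (delta method or bootstrap) from a model with clustering in one arm, pooled over 20 imputations.

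### As listed in the SAP, the Fagerström growth model has a random intercept as its sole participant-level random term, so the standard error of the time-by-condition test can be wrong in either direction

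*SAP*

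**What the plan says.** The SAP, a single section, sets out the growth model for the Fagerström score term by term:

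- Random and fixed parts: "The baseline was defined as the random intercept, and the model included fixed effects variables for time". Condition and the time-by-condition interaction are the other fixed effects.
- Time is "measured in months since the baseline assessment", so it is coded 0, 1 and 3.
- Tested term: "The interaction term estimates the change in the outcome from baseline to 3-month follow-up for the intervention condition relative to the control condition".
- Estimation: "Models were estimated with maximum likelihood using all available data".
- Clustering, stated for the models in general: "The models allowed for between-cluster variability in the outcomes solely within the intervention group". The SAP does not say whether this variability applies to level, to change over time, or to both.

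The protocol supplies the occasions. Section C.5.2: "Nicotine dependence will be measured at baseline and at each follow-up assessment using the Fagerström Test for Nicotine Dependence". Section C.2 places the follow-ups at 1 and 3 months. Section C.1 plans the evaluation "with a nationwide sample of 500 adults who are daily smokers", and C.2 allocates them equally to two arms.

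**The concern.** A participant random intercept with independent residuals is a compound-symmetry model: every occasion has the same variance and every pair of occasions the same correlation. The interaction compares change between arms, and the variance of change is what that restriction fixes.

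Equal correlation is doubtful in a cessation trial. Some participants will stop smoking and others will not, and some of those who stop will start again. Scores may drift apart over time, or diverge at one month and come back together by three. In the first case the pooled within-person residual captures only part of the real variation in change. In the second it can overstate it.

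The cluster term does not repair this. A group-level intercept shifts all of a member's scores equally and cancels out of change. A group-level slope would capture differences between groups, but not between participants within a group, and the control arm has no groups.

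At stake are the p-value and confidence interval for the one continuous outcome that the SAP analyses with this model. The logistic analyses of the dichotomous outcomes are not affected.

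**Working it through.** The documents give no standard error, correlation, standard deviation or significance level for this model, so there is no planned figure to reproduce. The check compares the variance that a random-intercept model reports with the true variance of the same estimate.

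**Inputs from the documents.** Times 0, 1, 3; three occasions; equal allocation; 500 participants.

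**Assumed.** Two-sided 5% test; no true effect; complete data unless stated; no group effect; model-based standard errors; all correlations, SDs and quit rates below. Variances are taken about the occasion means.

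**Formulas.** Mean time is 4/3, and Sxx = (−4/3)² + (−1/3)² + (5/3)² = 4.667. A participant's fitted slope has weights c = (t − 4/3)/Sxx = (−0.286, −0.071, 0.357). With S the true 3×3 covariance matrix:

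- true slope variance = c′Sc
- reported slope variance = W/Sxx, where W = [trace(S) − (sum of all entries of S)/3]/2 is the pooled within-person variance
- type I error = 2[1 − Φ(1.96 × √(reported/true))]

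The number per arm multiplies both variances equally and cancels from the ratio.

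**Worked case: correlations 0.75 (0–1), 0.65 (0–3), 0.70 (1–3), SD 1.**

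- True: 0.2143 + 2(0.0204×0.75 − 0.1020×0.65 − 0.0255×0.70) = 0.2143 − 0.1378 = 0.0765.
- Reported: W = [3 − (3 + 2×2.10)/3]/2 = 0.30, and 0.30/4.667 = 0.0643.
- True/reported = 1.19. The standard error is 1/√1.19 = 0.917 of its correct value, and type I error is 7.2%.

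| Correlations 0–1 / 0–3 / 1–3 | True/reported variance | Reported SE | Type I error |
|---|---|---|---|
| 0.70 / 0.70 / 0.70 | 1.00 | correct | 5.0% |
| 0.60 / 0.60 / 0.75 | 1.04 | 2% too small | 5.5% |
| 0.75 / 0.65 / 0.70 | 1.19 | 8% too small | 7.2% |
| 0.60 / 0.50 / 0.80 | 1.22 | 10% too small | 7.6% |
| 0.80 / 0.60 / 0.75 | 1.42 | 16% too small | 10.0% |
| the same, SD 1.0 / 1.1 / 1.25 | 1.48 | 18% too small | 10.7% |
| 0.65 / 0.70 / 0.70 | 0.92 | 4% too large | 4.1% |

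**Quitting and relapse.** Assume a between-person SD of 2, a residual SD of 1, and a 3-point lower score while quit. With 25% quit at one month, 12% at three months, and 60% of early quitters relapsed:

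- the variances are 5.00, 4 + 1 + 9×0.25×0.75 = 6.69, and 4 + 1 + 9×0.12×0.88 = 5.95
- the 1–3 month covariance is 4 + 9(0.25×0.40 − 0.25×0.12) = 4.63, and the other two are 4.00.

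| Quit at 1 month / 3 months; early quitters relapsed | True | Reported | Type I error |
|---|---|---|---|
| 12% / 15%; 30% | 0.335 | 0.322 | 5.5% |
| 15% / 15%; 50% | 0.342 | 0.344 | 4.9% |
| 20% / 12%; 50% | 0.308 | 0.336 | 4.1% |
| 25% / 12%; 60% | 0.312 | 0.358 | 3.6% |

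**Linear slope variation.** With residual variance s² and slope variance τ², the true variance is s²/4.667 + τ² and the reported variance is s²/4.667 + τ²/2. With s = 1:

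| Slope SD per month | SE ratio | Type I, formula | Simulated, complete data | Simulated, 75% complete |
|---|---|---|---|---|
| 0 | 1.00 | 5.0% | 5.4% | 5.0% |
| 0.3 | 0.92 | 7.0% | 7.2% | 6.3% |
| 0.5 | 0.86 | 9.4% | 9.6% | 9.9% |
| 0.8 | 0.79 | 12.1% | 13.3% | 15.1% |

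The simulations fitted the random-intercept model by maximum likelihood, 250 per arm, 1,000 runs each. The 75% follows the protocol's estimate in C.1 of how many participants will earn the bonus for completing all assessments. As τ² comes to dominate, the ratio falls to √(1/2) = 0.707 and type I error reaches 16.6%, the ceiling for complete data under linear slope variation.

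**The case against.** Three points on the other side have weight.

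First, the SAP nowhere says that the intercept is the sole random term. The sentence could mean merely that the intercept is located at baseline. A model with a random slope also carries a fixed effect of time, so listing time as fixed excludes nothing. A reader might infer that the SAP rules out a random slope; it does not. What stands is that the model is described term by term, with no slope, residual structure or robust standard error among the terms, so an analyst following the text would fit a random-intercept model.

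Second, a reader might infer that the standard error is too small and the p-value too optimistic. The documents do not support that as a fact. Having some participants quit and others not does not settle the sign: the relapse cases above make the test conservative, and in one (15% quit at both times, half of early quitters relapsed) the errors nearly cancel. This objection stands in full.

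Third, the sizes depend on chosen correlations, and the steepest fading gives the largest figures. That also stands; mild fading gives 5.5%.

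A reader might also take maximum likelihood estimation to be part of the fault. With about 500 participants, the difference between maximum and restricted likelihood is negligible for a participant-level covariance.

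**Conclusion.** The point holds in conditional form. If the model was fitted as listed, with model-based standard errors, its covariance structure is more restrictive than the test of change can safely bear. Type I error at a nominal 5% runs from about 5.5% to 11% under the assumed correlations where association fades with time, and from about 3.6% to 4.1% under the assumed patterns of early quitting followed by relapse. It is correct when variances and correlations are equal across the three occasions. Neither the direction nor the size can be read from the documents, and clustering was left out of the calculations. If a random slope, another covariance structure or a robust standard error was in fact used, the SAP omits a choice that determines the p-value and should state it.

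**What to change.** Fit the Fagerström growth model with an unstructured participant-level covariance over the three assessments in place of the random intercept, keep the intervention-arm cluster term, and base the interaction test on that fit. State the full random-effects and residual structure in the SAP, including whether the cluster term applies to level, change or both.

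A participant random slope for time is the alternative. It addresses the case in which the standard error is too small. It is less suited to relapse, because with a constant residual variance a linear random slope cannot produce a variance that peaks at one month, as in the relapse cases above. The unstructured form covers both directions.

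The unstructured matrix has six parameters against two for the random intercept, so four more; a random slope with its covariance adds two. Three occasions and about 500 participants support either. The SAP is written in the past tense, so this means a refit as well as revised wording, and possibly a slightly wider interval. No new data are needed. Restricted likelihood with Kenward-Roger degrees of freedom is not needed to correct this fault.
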